## Official Title of the study:

Analyses of maternal plasma cadmium, lead and vanadium levels in the diagnosis and severity of late-onset preeclampsia; A prospective and comparative study from Turkey

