### **1. Participant Flow**

#### **Recruitment Details**

This observational case-control study was conducted at the Department of Obstetrics and Gynecology, Cengiz Gokcek Public Hospital, Gaziantep, Turkey, between March 2018 and June 2019. The protocol was approved by the Ethics Committee for Clinical Research of Gaziantep University (reference no: 2019/36). The investigators included subjects consisted of women with a singleton pregnancy who were diagnosed as having late-onset preeclampsia between 34+0 and 41+0 weeks of gestation. Pregnant women with uncomplicated pregnancies were randomly selected to serve as controls. The study was conducted with 46 late-onset preeclampsia patients as study group and 46 patients with normal pregnancies as control group. All participants included in the study gave oral and written informed consent.

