**2. Baseline Characteristics**

To detect significant difference between groups according to lead levels with a moderate effect size (Cohen's  $d = 0.62$ ), minimum required sample size was estimated as 42 for each group ( $\alpha=0.05$ ,  $1-\beta=0.80$ ). Power analysis was performed by using G power package version 3.1. Kolmogorov Smirnov and Shapiro Wilk tests were used to test the normal distribution of data. For comparing groups (L-PrE/control) the student t-test was used for variables that have a normal distribution, and the Mann Whitney U test was used for variables that have not a normal distribution. The ROC analysis was applied for the determination of cut-off point for vanadium variable. Moreover, Spearman correlation test was used for the relationship of between variables. SPSS for Windows 22.0 and Medcalc programs were used for statistical analysis.  $p<0.05$  was accepted as statistical significance.

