**3. Outcome Measures**

Every participant in the study population underwent obstetric ultrasound examination and fetal-maternal assesment was carried out by one of the investigators. The obstetric anamnesis were obtained from all participants. The demographic data like age, gravidity, parity, body mass index (BMI) and gestational age were recorded. The gestational age was determined by calculation from the last menstrual period and supported by the ultrasonography measurements at first trimester of gestation. Maternal venous plasma samples were taken for measurement of cadmium, lead and vanadium levels after the diagnosis of L-PrE in outpatient clinic. These samples quickly centrifuged at 1,500 g for 10 min, plasma samples were seperated and stored at -80 C until the day of measurement. All patients with L-PrE were also hospitalized and their pregnancies were terminated. The samples of the control groups were obtained during the routine obstetrical care examination in the third trimester of pregnancy. Then, these pregnant women were followed-up until the delivery. Both groups were compared in terms of maternal age, BMI, week of gestation, gravida, parity, live born, systolic/diastolic blood pressure, total protein in spot urine sample, hemoglobin, hematocrit, platelet count, white blood cell count, urea, uric acid, albümin, blood urea nitrogen, creatinine, liver function tests (AST, ALT), lactic acid dehydrogenase, cadmium, lead and vanadium concentrions and infant weight at delivery. Small for gestational age (SGA) neonate was defined as birth weight <10th percentile for gestational age with Turkey's national nomogram as the reference for fetal growth. The samples were transferred within boxes in ice molds to Yozgat Bozok University Science and Technology Application and Research Center (Occupational and Environmental Toxicology Laboratory) for measuring heavy metal and trace element levels. The frequency of seafood consumption was divided into four categories: 2-3 per week, 1-2 per week, 1-2 per month, and rare. Smoking was classified into 3 groups (none, formerly smoker, and active smoking). Passive smoking was also categorized into 2 groups (no and yes). The education levels was classified into 4 groups (illiterate,

primary education, high school, and university). The residences of women was classified as rural and urban. Furthermore, the residences of women have divided either living near a busy street (around 100 metres) or not.

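### The title sets a diagnostic aim and a vanadium cut-off is derived, but only diagnosed cases and uncomplicated pregnancies were sampled, so diagnostic accuracy is unobserved

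*Protocol*

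**What the plan says.** The official title gives the purpose as "Analyses of maternal plasma cadmium, lead and vanadium levels in the diagnosis and severity of late-onset preeclampsia". The design is stated under Recruitment Details: "This observational case-control study was conducted at the Department of Obstetrics and Gynecology". Cases are women "who were diagnosed as having late-onset preeclampsia between 34+0 and 41+0 weeks of gestation". For the comparison group, "Pregnant women with uncomplicated pregnancies were randomly selected to serve as controls". The group sizes are 46 and 46.

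On sampling, section 3 (Outcome Measures) says of the cases: "Maternal venous plasma samples were taken for measurement of cadmium, lead and vanadium levels after the diagnosis of L-PrE in outpatient clinic". Of the controls it says: "The samples of the control groups were obtained during the routine obstetrical care examination in the third trimester of pregnancy".

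The statistical paragraph, printed under section 2 (Baseline Characteristics), adds: "The ROC analysis was applied for the determination of cut-off point for vanadium variable". It does not say which two groups this ROC analysis separates.

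Section 4 (Endpoints) lists three comparisons of metal levels: cases against controls, mild against severe cases, and SGA against non-SGA. It names no measure of diagnostic accuracy. Section 5 (Limitations and strengths) covers limited exposure and representativeness, sampling at one time point and the resulting limit on temporality, the lack of urinary levels, and residual confounding. It also records that women with systemic disease predating pregnancy were excluded. It does not discuss the choice of uncomplicated controls.

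**The concern.** A diagnostic question concerns women in whom the diagnosis is open: preeclampsia is suspected and has to be told apart from whatever else could explain the findings. Neither sampled group represents them. The cases had their diagnosis before blood was drawn, and the controls had pregnancies in which it was not in doubt.

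This contrast can answer whether metal levels differ between established late-onset preeclampsia and uncomplicated pregnancy. It cannot show whether a metal level helps to decide an uncertain case. With a diagnostic title and a ROC cut-off in the same document, the vanadium threshold could easily be reported, or read, as a diagnostic one. That conclusion would be unsupported even if every number were computed correctly.

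**Working it through.** **Step 1: aim, design and endpoints side by side.**

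| Element | Where | What it supports |
|---|---|---|
| Metals in diagnosis and severity | Title | A diagnostic claim |
| ROC cut-off for vanadium | Section 2 | A classification rule; contrast not named |
| Diagnosed cases, sampled after diagnosis | Recruitment Details; section 3 | Levels in established disease |
| Uncomplicated pregnancies only | Recruitment Details | Levels where the diagnosis is not in doubt |
| Comparisons of levels | Section 4 | Association |
| Choice of controls | Section 5 | Not mentioned |

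Only the title and the ROC analysis point to diagnosis. The design and the endpoints support association.

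**Step 2: reproduce the plan's own figure.** Section 2 gives d = 0.62 for lead, α = 0.05, power 0.80 and 42 per group.

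- Two-sided normal approximation: n = 2(1.960 + 0.842)²/0.62² = 40.8, so 41.
- Two-sample t-test (noncentral t): 41.82, so 42, as stated. Power is 80.2% with 42 per group and 83.7% with 46.

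The figure reproduces. It sizes the study for a difference in mean lead, not for sensitivity, specificity or AUC.

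**Step 3: an illustration of how the choice of controls can matter.** The following are assumptions, not facts from the protocol: normal levels with equal variance; the lead effect d = 0.62 borrowed for a generic metal, because no effect size is given for vanadium; and suspected-but-unconfirmed women whose mean lies a fraction s of the way from the control mean to the case mean.

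Against uncomplicated controls:

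- AUC = Φ(d/√2) = Φ(0.438) = 0.669. With 46 + 46 women the Hanley–McNeil standard error is 0.056, giving an approximate 95% interval of 0.56 to 0.78.
- At the midpoint cut-off d/2, sensitivity = specificity = Φ(0.31) = 62.2%.

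Against suspected women, at the same cut-off, specificity = Φ(d/2 − s·d) and AUC = Φ((1 − s)d/√2):

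| s | Specificity | AUC |
|---|---|---|
| 0 | 62.2% | 0.669 |
| 0.25 | 56.2% | 0.629 |
| 0.50 | 50.0% | 0.587 |
| 0.75 | 43.8% | 0.544 |
| 1 | 37.8% | 0.500 |

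Three things follow.

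- Sensitivity stays at 62.2% throughout, because at a fixed cut-off it depends on the cases alone.
- The 50% at s = 0.50 is true by construction: a symmetric group centred on the cut-off always gives 50%, whatever d is.
- A negative s, with suspected women further from the cases than the controls are, reverses the direction. At s = −0.25, specificity is Φ(0.31 + 0.155) = 67.9%.

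The protocol gives nothing from which to choose s. The table shows the mechanism; it does not estimate the effect in this study.

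**The case against.** The best defence is that this is already an association study. The endpoints compare levels, the sample size is for a mean difference, section 5 speaks of associations, and no diagnostic conclusion is drawn anywhere in the document. A case-control contrast is a legitimate early step for a biomarker. Most of this is right, and it is why the remedy is confined to wording. It does not explain why the title claims diagnosis or why a cut-off is derived, and section 5 does not warn the reader what that cut-off means. A separate analysis plan could name the ROC contrast, but it could not supply women who were never sampled.

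Several stronger readings are tempting and are not supported:

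- **That the cut-off is certain to look too specific.** This depends on metal levels in women who were not sampled. There is no loss if those levels match the controls, and the direction can reverse.
- **That sensitivity is inflated by the choice of controls.** At a fixed cut-off it is not affected.
- **That the sample holds only the two extremes of disease.** Section 4 divides the cases into mild and severe, so the gap is on the control side.
- **That the ROC certainly uses cases against controls.** This is the likely reading, but section 2 does not say so. A cut-off for mild against severe disease would not involve the uncomplicated controls at all.
- **That the figures at d = 0.62 describe the planned cut-off.** That effect size is for lead; the only cut-off is for vanadium.

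**Conclusion.** The point stands in a limited form. The title sets an aim that the sampled groups cannot meet: accuracy among women with suspected but unconfirmed preeclampsia is unobserved, and the protocol does not say so. This part rests on the documents alone and needs no numerical assumption.

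The second part is conditional. If the vanadium ROC contrasts cases with uncomplicated controls, its AUC and specificity may be too favourable for women with suspected disease. The documents do not allow the size to be estimated, and it may be nil. In the illustration, specificity runs from 62% with no shift to 44% with a 75% shift towards the cases, under assumed normality, equal variance and an effect size borrowed from lead.

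The comparisons of metal levels in section 4 are not affected. What changes is what the study may conclude.

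**What to change.** 1. In the title and wherever the aim is stated, replace the reference to diagnosis with association with established late-onset preeclampsia.
2. In the statistical paragraph of section 2, name the two groups that the vanadium ROC analysis separates. State that the cut-off is exploratory, that it describes separation of those sampled groups only, and that it will not be reported as a diagnostic threshold or as diagnostic accuracy.
3. In section 5, add that the controls were uncomplicated pregnancies only, so that performance among women with suspected but unconfirmed preeclampsia was not studied.

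This needs no new patients, assays or analyses, which matters because the protocol describes recruitment in the past tense (March 2018 to June 2019). The cost is a less favourable claim.

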### **1. Participant Flow**

#### **Recruitment Details**

This observational case-control study was conducted at the Department of Obstetrics and Gynecology, Cengiz Gokcek Public Hospital, Gaziantep, Turkey, between March 2018 and June 2019. The protocol was approved by the Ethics Committee for Clinical Research of Gaziantep University (reference no: 2019/36). The investigators included subjects consisted of women with a singleton pregnancy who were diagnosed as having late-onset preeclampsia between 34+0 and 41+0 weeks of gestation. Pregnant women with uncomplicated pregnancies were randomly selected to serve as controls. The study was conducted with 46 late-onset preeclampsia patients as study group and 46 patients with normal pregnancies as control group. All participants included in the study gave oral and written informed consent.

#### **Pre-assignment Details**

The authors firstly were assessed the recruited people to ensure meeting the inclusion and exclusion criteria.

The inclusion criteria were made according to the official documents.

**Arm/Group Information \***

There are two groups in the study.

**Arm/Group Title \***

Preeclampsia group

Control group

**2. Baseline Characteristics**

To detect significant difference between groups according to lead levels with a moderate effect size (Cohen's  $d = 0.62$ ), minimum required sample size was estimated as 42 for each group ( $\alpha=0.05$ ,  $1-\beta=0.80$ ). Power analysis was performed by using G power package version 3.1. Kolmogorov Smirnov and Shapiro Wilk tests were used to test the normal distribution of data. For comparing groups (L-PrE/control) the student t-test was used for variables that have a normal distribution, and the Mann Whitney U test was used for variables that have not a normal distribution. The ROC analysis was applied for the determination of cut-off point for vanadium variable. Moreover, Spearman correlation test was used for the relationship of between variables. SPSS for Windows 22.0 and Medcalc programs were used for statistical analysis.  $p<0.05$  was accepted as statistical significance.

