#### **4. Endpoints of the study:**

The primary outcome in these analyses was to compare cadmium, lead and vanadium levels in L-PrE group and control group.

The secondary outcome was to compare the cadmium, lead and vanadium levels in mild L-PrE group and severity L-PrE group.

Tertiary outcome was to compare the cadmium, lead and vanadium levels in SGA group and non-SGA group.

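### The primary metal comparison is unadjusted, although cases and controls have differently defined blood-sampling windows and controls may have been sampled earlier in pregnancy

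*Protocol*

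**What the plan says.** The Endpoints section (section 4) states: "The primary outcome in these analyses was to compare cadmium, lead and vanadium levels in L-PrE group and control group". The between-group methods are in section 2, Baseline Characteristics: "For comparing groups (L-PrE/control) the student t-test was used for variables that have a normal distribution". Metals that fail normality go to a rank-based alternative, the Mann-Whitney test. The other methods named there are normality tests, a ROC analysis for vanadium, and correlation: "Moreover, Spearman correlation test was used for the relationship of between variables". No regression, covariate, stratification or matching is mentioned.

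Timing is set in two places. Recruitment Details (section 1) describes cases as "diagnosed as having late-onset preeclampsia between 34+0 and 41+0 weeks of gestation", and Outcome Measures (section 3) places their blood sample after that diagnosis. For controls, Recruitment Details says "Pregnant women with uncomplicated pregnancies were randomly selected to serve as controls", and Outcome Measures says "The samples of the control groups were obtained during the routine obstetrical care examination in the third trimester of pregnancy".

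Gestational age is collected: "The demographic data like age, gravidity, parity, body mass index (BMI) and gestational age were recorded". Week of gestation is also among the variables compared between the two groups.

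**The concern.** A case cannot be sampled before 34+0 weeks. Under the text a control can be, because the third trimester begins before 34 weeks and no lower limit or matching on week is stated. Controls may therefore have been sampled earlier on average.

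If they were, and if a metal's plasma level rises or falls with gestational week, a t-test or Mann-Whitney test attributes that change to preeclampsia. Depending on direction, this can create a difference that does not exist or hide one that does. Both conditions must hold for there to be any bias, and the protocol establishes neither. Comparing week between groups, or correlating week with metal level, could reveal the problem. Neither step removes it from the case-control contrast.

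**Working it through.** **Inputs from the protocol.** Effect size d = 0.62 for lead, α = 0.05, power 0.80 and 42 per group required (section 2); 46 per group enrolled (section 1); case window 34+0 to 41+0 weeks (section 1); control window the third trimester (section 3).

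**Assumptions.** The protocol gives no control weeks by group and no metal-by-week slope. I take cases as spread evenly over 34–41 weeks and controls as spread evenly from 34, 32, 30 or 28 weeks to 41. The 28-week start is my assumption, since the protocol does not define the third trimester.

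**1. The plan's own figure.** Two-sample t-test, noncentral t, two-sided α = 0.05, d = 0.62: 42 per group gives power 0.802, so the stated number is reproduced. With 46 per group, noncentrality is 0.62 × √(46/2) = 2.97 on 90 df, and power is 0.837. The sample size is not in dispute.

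**2. Possible gap in weeks.** Mean case week is (34 + 41)/2 = 37.5. Within-group SD of week is √[(7²/12 + w²/12)/2], where w is the width of the control window.

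| Controls from | Mean control week | Gap (weeks) | Within-group SD | Gap in SDs |
|---|---|---|---|---|
| 34 | 37.5 | 0 | 2.02 | 0 |
| 32 | 36.5 | 1.0 | 2.33 | 0.43 |
| 30 | 35.5 | 2.0 | 2.66 | 0.75 |
| 28 | 34.5 | 3.0 | 3.01 | 1.00 |

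**3. Effect on the unadjusted test.** Spurious shift = slope (SD per week) × gap (weeks). The rejection probability is the noncentral-t power at that shift. When the shift opposes a true effect, power is evaluated at 0.62 minus the shift.

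| Shift (SD) | False-positive rate, no true effect | Power if shift opposes d = 0.62 |
|---|---|---|
| 0 | 5.0% | 83.7% |
| 0.1 | 7.6% | 69.4% |
| 0.2 | 15.8% | 51.3% |
| 0.3 | 29.6% | 33.0% |

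A 10% false-positive rate needs a shift of 0.137 SD, which is a slope of 0.137, 0.069 or 0.046 SD per week for a gap of 1, 2 or 3 weeks. At a slope of 0.03 SD per week, the shifts are 0.03, 0.06 and 0.09 SD and the rates only 5.2%, 5.9% and 7.1%.

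**4. Does adjustment help?** Simulation with no true effect, 20,000 runs, slope 0.10 residual SD per week:

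| Controls from | Unadjusted | Week-adjusted |
|---|---|---|
| 34 | 5.2% | 5.2% |
| 32 | 7.5% | 4.8% |
| 30 | 15.0% | 4.9% |
| 28 | 28.2% | 5.1% |

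The unadjusted rates are close to step 3. They differ slightly because the simulation scales the slope to the residual SD rather than the total within-group SD.

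**5. What adjustment costs in power.** With week in the model there are 89 df and noncentrality is 0.62 × √23 × √(1 − R²), where R² = (g²/4)/(1 + g²/4) and g is the gap in within-group SDs.

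| g | R² | Power if week does not predict the metal | Power if week explains 10% of within-group variance |
|---|---|---|---|
| 0.5 | 0.059 | 81.4% | 85.3% |
| 0.75 | 0.123 | 78.6% | 82.7% |
| 1.0 | 0.200 | 74.9% | 79.2% |

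**6. Restricting to 34+0 weeks or later.** Controls remaining are 46 × 7/9 ≈ 36, 46 × 7/11 ≈ 29 or 46 × 7/13 ≈ 25 for windows starting at 32, 30 or 28 weeks. Against 46 cases, power at d = 0.62 is 78.6%, 73.2% or 69.2%.

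**The case against.** The two windows do not contradict each other, because the case window lies inside the third trimester and nothing says controls were in fact sampled earlier. Bias needs both a gap in weeks and a trend with week, and the protocol gives a figure for neither. The 29.6% rests on the widest window and a slope of 0.10 SD per week; with smaller slopes the rate stays near 5%. All of this stands, and it is why the size is given as a range that includes no effect.

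A separate analysis plan might add adjustment. That lowers confidence, but the protocol does name its between-group tests, and they are unadjusted.

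The Limitations and strengths section already concedes residual confounding and a single sampling time point. The concession is general. Gestational week is not among the factors listed there as similar between groups, and the single-time-point remark concerns exposure history and temporality, not a difference in timing between groups.

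The strongest practical objections concern the remedy. The recorded gestational age might be that at delivery, which would be the wrong covariate. The text reads as if the study is complete, so changing the basis of the conclusion could come after results were seen. Adjustment can take power below 80%. In the widest scenario 6/13, or about 46%, of controls lie where there are no cases, so adjustment leans on a linear trend. These points limit the fix rather than defeat it, and they call for a check of the covariate, disclosure of timing and a restricted analysis.

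**Conclusion.** The concern holds and should be fixed, with medium confidence. The protocol fixes an unadjusted primary comparison while defining the sampling windows of the two groups differently, and it leaves the recorded gestational age out of that comparison.

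Whether any bias exists cannot be told from the document. If control weeks match case weeks, or the metals do not vary with week, there is none. Under the even-window assumptions the unadjusted false-positive rate runs from the nominal 5% to about 30%, and the upper end needs both the widest control window and a steep slope. The same shifts in the opposite direction would take power at d = 0.62 from 83.7% to as little as 33.0%.

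**What to change.** Confirm that the recorded gestational age is that at blood sampling, and report its median and range by group. For each metal, fit a regression of concentration (log-transformed if skewed) on group and gestational week at sampling, with a 95% confidence interval, and show it beside the unadjusted test. Base the case-control conclusion on the week-adjusted estimate. If unadjusted results were known when this was added, say so. If any controls were sampled before 34+0 weeks, add a supportive analysis limited to women sampled at 34+0 weeks or later. Adjustment for other recorded covariates is optional, as sensitivity analysis.

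The cost is one degree of freedom and one regression per metal, with no new data if the recorded week is the right one; otherwise sampling dates must be recovered. When the groups' weeks differ there is also the power loss shown above, which can fall below the planned 80%. Adjustment assumes a common linear trend with week, and it does not cure the fact that cases were sampled after diagnosis.

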Venous blood sampled from the antecubital veins for measuring plasma concentration of cadmium, lead and vanadium levels. The three metals (cadmium, lead and vanadium) were measured using inductively coupled plasma-mass spectrometry (Thermo Scientific ICAPQc, USA).

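### The ROC cut-off analysis is fixed to vanadium alone without a reason, and accuracy quoted for that cut-off in the same 92 women would on average be optimistic (minor; cheap to improve)

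*Protocol*

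**What the plan says.** The only sentence on diagnostic accuracy is in Protocol section 2, Baseline Characteristics: "The ROC analysis was applied for the determination of cut-off point for vanadium variable". It names one metal, gives no reason, and does not mention cadmium or lead.

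Elsewhere the three metals stand on an equal footing:

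- Title: "Analyses of maternal plasma cadmium, lead and vanadium levels in the diagnosis and severity of late-onset preeclampsia".
- Section 3, Outcome Measures: "The three metals (cadmium, lead and vanadium) were measured using inductively coupled plasma-mass spectrometry". The same section lists all three among the variables compared between the groups.
- Section 4, Endpoints: "The primary outcome in these analyses was to compare cadmium, lead and vanadium levels in L-PrE group and control group". The secondary and tertiary endpoints also name all three, without ranking: "The secondary outcome was to compare the cadmium, lead and vanadium levels in mild L-PrE group and severity L-PrE group" and "Tertiary outcome was to compare the cadmium, lead and vanadium levels in SGA group and non-SGA group".

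The one metal given a special role elsewhere is lead, on which the sample size rests.

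On the groups, the Arm/Group entries in section 1 name two, preeclampsia and control. The test description in section 2 uses that contrast: "For comparing groups (L-PrE/control) the student t-test was used". Recruitment Details describes a single sample: "The study was conducted with 46 late-onset preeclampsia patients as study group and 46 patients with normal pregnancies as control group". No separate validation sample is described.

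**The concern.** A study whose title puts three metals to the diagnosis of late-onset preeclampsia plans a diagnostic threshold for only one of them. A reader of the results could not tell whether cadmium or lead discriminates better, worse or equally well, because the plan asks for no matching figure. The measurements needed to answer that are already in hand.

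The second issue is how the threshold would be judged. A cut-off chosen to perform well in a sample tends to look better in that sample than in new women. With 46 per group and no second sample, sensitivity and specificity quoted beside the cut-off would carry that bias unless it is corrected. At stake is the credibility of a supplementary threshold, not the primary comparison of levels.

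**Working it through.** **1. The plan's own calculation.** The protocol has one design figure: 42 per group for lead at d = 0.62, α = 0.05, power 0.80. The normal approximation gives 2 × (1.960 + 0.842)² / 0.62² = 2 × 7.85 / 0.384 = 40.8, so 41. The exact two-sided t-test gives 42 (power 0.802). The figure reproduces. At the 46 per group recruited, power for the same effect is 0.837. None of this bears on the ROC, for which the protocol gives no figure.

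**2. Inputs for the optimism check.**

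- From the protocol: 46 cases and 46 controls. The value d = 0.62 is also the protocol's, but for lead; it is borrowed here as one point in a range.
- Assumed: normal values with equal SD, higher in cases; a cut-off that maximises the Youden index J = sensitivity + specificity − 1; a true vanadium effect d between 0 and 1.5.

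**3. Method.** In each of 20,000 simulated studies per setting, the cut-off c with the largest J is found. Apparent J is its value in those 92 women. True J is what the same c gives in the population: Φ(d − c) + Φ(c) − 1, where Φ is the standard normal distribution function, controls have mean 0 and cases mean d.

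**4. Results (averages).**

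| d | Apparent J | True J | Excess |
|---|---|---|---|
| 0 | 0.120 | 0.000 | 0.12 |
| 0.3 | 0.214 | 0.101 | 0.11 |
| 0.62 | 0.324 | 0.222 | 0.10 |
| 1.0 | 0.451 | 0.362 | 0.09 |
| 1.5 | 0.603 | 0.527 | 0.08 |

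At d = 0.62 this is an apparent sensitivity of about 0.69 against a true 0.63, and an apparent specificity of about 0.64 against 0.59. Across the range, each of the two is overstated by roughly 3 to 7 percentage points.

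**5. An average, not a certainty.** At d = 0.62 the apparent J fell below the true J in about 10% of simulated studies; at d = 1.5, in about 16%.

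**6. What a correction achieves.** A bootstrap with 200 resamples that repeats the cut-off choice in each resample was run on 500 simulated studies. It gives, as apparent / corrected / true J: 0.122 / 0.044 / 0.000 at d = 0; 0.324 / 0.255 / 0.221 at d = 0.62; 0.607 / 0.554 / 0.529 at d = 1.5. The correction removes most of the optimism but not all of it.

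**7. Precision of an AUC at this size.** Under the same normal model, d = 0.62 corresponds to AUC = Φ(0.62/√2) = 0.67. By Hanley–McNeil with A = 0.67:

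- Q₁ = A/(2 − A) = 0.504 and Q₂ = 2A²/(1 + A) = 0.538.
- Variance = [A(1 − A) + 45(Q₁ − A²) + 45(Q₂ − A²)] / 46² = (0.221 + 2.469 + 3.992) / 2116 = 0.00316.
- SE = 0.056, and the 95% CI is 0.67 ± 1.96 × 0.056, that is 0.56 to 0.78.

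**The case against.** The strongest reply is that examining one marker's cut-off in a supplementary analysis is a choice and not an error, and that the cut-off rule and internal validation are ordinary content for an analysis plan that is not on view. The second part stands: the absence of a cut-off rule or a validation method here is not a fault of the protocol. The first part stands in so far as nothing is contradicted. But the restriction to one metal is not deferred to another document. This document states it, without a reason, against a title and endpoints that treat the three metals alike.

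Several stronger readings are tempting, and the protocol does not support them.

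- *Vanadium was picked because it looked best in the data.* The past tense and the lead-based sample size are compatible with that, but nothing shows it. Estimates of extra bias from a best-of-three choice would therefore rest on an unshown premise.
- *The ROC has no defined contrast.* The sentence itself does not name one. But the protocol declares two groups, and the test description just before it uses preeclampsia against control, so that reading is natural. Spelling it out is a matter of detail. Optimism figures for mild against severe disease, or for small-for-gestational-age infants, would need subgroup sizes that the protocol does not give.
- *The primary outcome is contradicted.* It is not. The primary outcome compares levels, and all three metals are compared.
- *Any quoted accuracy must be too high.* It is too high on average only; in a minority of studies it would be too low. The protocol quotes no sensitivity, specificity, AUC or threshold, so no reported figure is wrong.

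**Conclusion.** The point holds as a minor one. The protocol fixes its only diagnostic analysis to vanadium without giving a reason, so cadmium and lead would have no comparable discrimination figure. On the natural contrast, a cut-off found and assessed in the same 92 women would on average overstate the Youden index by about 0.08 to 0.12. The direction on average follows from choosing and judging the cut-off in one sample. The size rests on normal data with equal SD, the Youden rule and an assumed vanadium effect, none of which the protocol gives for this analysis. The ROC is part of no endpoint, so the primary, secondary and tertiary comparisons of levels are unaffected.

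**What to change.** In the statistical paragraph of section 2:

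- Run the ROC for cadmium, lead and vanadium on preeclampsia against control, and report each AUC with its 95% CI.
- For any cut-off reported, give sensitivity and specificity with a bootstrap optimism correction that repeats the cut-off choice in every resample.
- Describe the cut-off as exploratory.

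The cost is a short extra analysis on measurements already made, with no new samples. The price is less favourable accuracy figures and wide intervals, as the AUC example shows. Some optimism would remain after the correction, which is why the exploratory label is needed as well.

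### Will the planned Spearman correlations mistake the case-control split for a relation between metals and disease severity?

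*Protocol*

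**What the plan says.** The statistical paragraph in Protocol section 2 (Baseline Characteristics) sets out the case-control comparisons by t-test or Mann-Whitney test and a ROC analysis for vanadium. It then adds: "Spearman correlation test was used for the relationship of between variables". The significance threshold is 0.05. Nothing says which variables are paired, or whether the correlations run over all women or within one group.

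The sample is described under Recruitment Details: "The study was conducted with 46 late-onset preeclampsia patients as study group and 46 patients with normal pregnancies as control group". Cases were "diagnosed as having late-onset preeclampsia between 34+0 and 41+0 weeks of gestation". For the comparison group, "Pregnant women with uncomplicated pregnancies were randomly selected to serve as controls".

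Section 3 (Outcome Measures) includes "systolic/diastolic blood pressure, total protein in spot urine sample" in a list of variables on which the two groups are compared. It does not mention correlation there. Section 4 (Endpoints) states the secondary outcome: to "compare the cadmium, lead and vanadium levels in mild L-PrE group and severity L-PrE group". No correlation appears among the primary, secondary or tertiary outcomes.

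**The concern.** Women are in this study because they do or do not have preeclampsia. Blood pressure, urinary protein and several laboratory values can therefore be expected to fall into two clusters. Any metal whose level also differs between the groups will then correlate with those values over the combined sample, even if there is no relation among cases or among controls. Nothing in the Spearman sentence rules out pooling.

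The title names severity as well as diagnosis. A pooled correlation of lead with systolic pressure could be read as a dose-severity relation when it only repeats the primary comparison in another form. Multiplicity adds to the worry: section 3 lists many variables, and every one could be paired with each of three metals at 0.05.

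**Working it through.** **The plan's own figure.** The only calculation in the protocol is the sample size: "minimum required sample size was estimated as 42 for each group" (d = 0.62, alpha 0.05, power 0.80). A two-sided t-test by the noncentral t distribution gives 41.82, rounded up to 42, so the figure reproduces. Power is 0.80 at 42 per group and 0.84 at the 46 recruited. The protocol gives no figure for the correlations.

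**Inputs for the check.** From the protocol: 46 + 46 women, d = 0.62 (planned for lead only), threshold 0.05. Assumed, because the protocol has no figure: normal data, zero correlation inside each group, and a marker that separates the groups by 1 to 6 within-group SD.

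**Expected pooled correlation.** With group shifts d1 (metal) and d2 (marker), both in within-group SD, and 1:1 groups, the pooled Pearson correlation is

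r = (d1·d2/4) / √[(1 + d1²/4)(1 + d2²/4)].

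With d1 = 0.62, 1 + d1²/4 = 1.0961.
- d2 = 1: 0.155 / √(1.0961 × 1.25) = 0.13
- d2 = 2: 0.31 / √(1.0961 × 2) = 0.21
- d2 = 4: 0.62 / √(1.0961 × 5) = 0.26

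The simulated mean Spearman values are 0.13, 0.21 and 0.25, in close agreement.

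**How often p < 0.05, pooled over 92 women** (4,000 simulated studies per cell):

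| Metal difference d | Marker 1 SD | 2 SD | 4 SD | 6 SD |
|---|---|---|---|---|
| 0 | 5% | 6% | 5% | 6% |
| 0.2 | 7% | 11% | 13% | 13% |
| 0.4 | 14% | 28% | 35% | 37% |
| 0.62 | 25% | 55% | 69% | 69% |
| 1.0 | 50% | 91% | 98% | 98% |

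Within the 46 cases alone, the test stays at about 5% in every setting. The mechanism is real, but it needs a true group difference in that metal and grows with that difference. Without one, the pooled test holds its level.

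**Multiplicity.** Section 3 lists 22 non-metal variables for the group comparison, counting systolic and diastolic pressure separately and AST and ALT separately. Then 22 × 3 = 66 pairs, and 66 × 0.05 = 3.3 expected false positives if every pair were tested and none were related. The protocol does not link that list to the Spearman test. Several entries (age, BMI, gravidity, parity) are not severity markers. The 66 is a ceiling on one reading, not a planned number of tests.

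**Does any stated conclusion depend on it?** The primary outcome is a direct case-control comparison of the metals. The secondary outcome compares mild with severe disease inside the case group, so a shift between cases and controls cannot create a difference there. The tertiary outcome compares metals by SGA status. None of the three uses a correlation coefficient.

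**The case for a change.** The best argument for a change is that the Spearman sentence follows directly on the case-control tests and carries no restriction, so all 92 women is at least as natural a reading as cases only. On that reading the analysis is confounded by case status, and to a material degree at the protocol's own planning effect. The remedy would cost one sentence and no new data: within-case or group-adjusted correlations for a short list of markers, with wider intervals as the price.

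The arithmetic in this argument stands, and so does the warning about how to read any pooled coefficient. What fails is the step from silence to error. Within-case correlation fits the sentence equally well. The pairs could also be metal with metal, metal with birth weight, or metal with the ordinal exposure items in section 3. That women were selected on blood pressure and proteinuria is a plausible inference from the diagnosis, but the document does not state it. The effect of 0.62 is a planning value for lead, and nothing supports it for cadmium or vanadium.

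**Conclusion.** No change to the plan follows. The protocol leaves open the pairs and the analysis set of a secondary, exploratory correlation. A protocol commonly leaves that to the SAP, which may exist but is not shown. An analyst who knows the sample is case-control would run disease-marker correlations within the 46 cases or adjust them for group, and the protocol's wording allows this.

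If such correlations were pooled, a spurious signal would be likely only for a metal that truly differs between groups. At d = 0.62, about 25% of studies would be significant at 1 SD of marker separation and 55-69% at 2 SD or more. At d = 0.4 the range is 14-37%, and at d = 0 it is about 5%. These figures rest on normal data, zero within-group association and assumed separations. Even then the result would repeat the primary comparison. The stated severity question is answered inside the case group and is unaffected.
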